8.4 Exclusion Criteria

Each potential patient must be screened to ensure they do not meet any of the following exclusion criteria. This screening is based on known medical history and data available at the time of eligibility determination and enrollment.

1. Significant disease of the ipsilateral common carotid artery on routine CTA
2. Presence of a cervical ICA loop or other high-risk anatomical features of the ICA on routine CTA, that may preclude the use of the NOVIS NPS
3. Any active or recent hemorrhage within the past 30 days
4. Embolectomy contraindications
 - a. Pre-stroke mRS ≥ 2
 - b. NIHSS ≤ 5
 - c. ASPECTS ≤ 5
5. IV tPA has been or is being administered
6. Last known well > 24 hours ago
7. Known history of severe head injury within past 90 days with residual neurological deficit, as determined by medical history
8. Patient has an isolated hemisphere, defined as intracranial circulation that is fed only by the ipsilateral internal carotid artery and may be detected on prior CTA
9. Known history of neurological or psychiatric disease that would confound the neurological or functional evaluations, e.g., dementia with prescribed anti-cholinesterase inhibitor (e.g., Aricept)
10. Presumed septic embolus, suspicion of bacterial endocarditis or cerebral vasculitis
11. Known history of ipsilateral severe intracranial atherosclerotic disease ($\geq 70\%$ stenosis) documented on prior imaging
12. Patient is known to have an active COVID-19 infection
13. Female who is pregnant or lactating at time of admission
14. Current participation in another investigational drug or device study.
15. Evidence of any other disease or condition expected to compromise survival or ability to complete the endovascular procedure or follow-up assessments during the 90-day follow-up period (e.g. methamphetamine, cocaine, or other recreational drug use)
16. Patient has recurrent or metastatic malignancy or cancer
17. Known history of hemorrhagic diathesis or coagulation factor deficiency
18. Known risks for paradoxical embolism, including intracardiac right-to left shunt (e.g., PFO, ASD, VSD) or history of pulmonary embolism or deep vein thrombosis
19. Patients that have undergone a transradial or transbrachial mechanical thrombectomy attempt prior to enrollment

9 Patient Enrollment

A patient is considered enrolled after:

- 1) written informed consent is obtained,
- 2) meeting all inclusion and none of the exclusion criteria,
- 3) failed transfemoral therapy

Patients who are screened but do not meet all study criteria are considered screen failures and will not be enrolled and no further follow-up assessments will be conducted.

9.1 Patient numbering

Patients will be identified by a Patient Identification (ID) number, which is a combination of the specified site number and a sequential number assigned by the site. The Patient ID will consist of a 3-digit number and will be consecutively assigned upon enrollment in the study.

9.2 Patient discontinuation

Where possible, every effort should be made for a patient to remain in the study until completion of the required follow-up period. However, if needed the patient's participation in the study may be discontinued at any time during the study. If this occurs, the reason for discontinuation should be documented in the source documentation, and the appropriate Case Report Form (CRF) must be completed. Factors leading to patient discontinuation may include, but are not limited to the following:

- **Patient Withdrawal:** Patient participation in a clinical trial is voluntary and the patient may discontinue participation (refuse all subsequent testing and follow-up) or withdraw their consent from the study at any time without affecting their future medical treatment or benefits.
- **Investigator Termination:** The Investigator may terminate the patient's participation without regard to the patient's consent if the Investigator believes it is medically necessary.
- **Lost to Follow-up:** A patient will be considered lost to follow-up after three unsuccessful, documented attempts have been made to contact the patient.
- **Death of Patient:** Upon notification of the death of the patient, the study site will be responsible for notifying Sponsor within 24 hours (refer to Section 12.2):

10 Study Procedures

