10.3.3 Establishment of Transcarotid Flow Reversal

The type of anesthesia used during the procedure is left to the discretion of the Investigator and will be documented on the CRFs. Should the investigator choose to start with moderate sedation conversion to general anesthetic should only occur if the Investigator deems it necessary. The type of anesthesia used will be documented in the CRFs.

After completing confirmatory duplex ultrasound, access to the common carotid artery cephalad to the clavicle will be gained using surgical techniques.

Investigators are to follow the NOVIS Transcarotid Neuroprotection System (NPS) Instructions for Use (IFU) for setting up and establishing the reverse flow circuit. Upon placement of the NOVIS system and prior to clamping the CCA, the differential in pressure causes some blood to flow between the CCA and femoral vein. At this point, there is still some antegrade flow in the CCA and therefore the carotid and cerebral vasculature is not “protected”. Once the CCA is clamped below the arterial sheath of the system on the Low flow setting, the NPS should remain on Low flow setting and switch to High flow upon the introduction of interventional tools through the completion of the procedure. Upon initial set-up of the device a pressurized, heparinized saline drip is connected to the 3-way stopcock on the side arm of the rotating hemostasis valve.

Any adverse events that are observed after establishing reverse flow will be followed through study exit.

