11.4 Patient Flow Diagram

[figure not shown]

Image also provided in Appendix 5.

12 Adverse Events

Adverse event (AE) data will be collected and recorded from index procedure through 90-day follow-up period (or until patient discontinuation) for all enrolled patients on the Adverse Event CRF. At each evaluation, the Investigator or coordinator will determine whether an adverse event has occurred based on, but not limited to reports from the study patient, observed by the investigator or coordinator or documented in the medical record. For the purpose of this protocol, an adverse event is any untoward medical occurrence in a study patient, which may or may not have a causal relationship with the study device. It includes any pre-existing condition that increases in severity or frequency or any new events that occur after the index procedure. An elective procedure for a pre-existing condition (that has not worsened) is not considered an AE.

Event, date of onset, duration, severity, seriousness, treatment, outcome and relationship to the device or procedure will be recorded on the Adverse Event CRF and cross-tabulated according to:

- Severity (Mild, Moderate, Severe)
- Seriousness (Serious Adverse Event (SAE), Non-serious AE)
- Serious Adverse Device Effect (SADE)
- Unanticipated Adverse Device Effect (UADE)
- Procedure-Relatedness (Not Related, Possibly Related, Probably Related, Causal/Related)
- Device-Relatedness (Not Related, Possibly Related, Probably Related, Causal/Related)

Anticipated AEs have been listed in Section 23.1, 23.2, 23.3 & 23.4, and all AEs will be monitored until they are adequately resolved or explained at the end of the study follow-up period. Beyond the routine annual reports, interim progress report will be provided every three months to FDA.

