12.2 Serious Adverse Events

When an adverse event meets the definition for serious adverse event, it should be considered as such and reported immediately (within 24 hours) of becoming aware of the event to the Sponsor and recorded in the source documentation. The SAE should be further reported to the reviewing IRB per hospital IRB requirements. An adverse event is considered serious if the event:

- Leads to death;
- Leads to a serious deterioration in the health of the patient that:
 - Results in life-threatening illness or injury;
 - Results in permanent impairment of a body structure or a body function;
 - Requires inpatient hospitalization or prolongation of existing hospitalization;
 - Results in medical or surgical intervention to prevent permanent impairment to a body structure or a body function.

An Adverse Event form will be completed promptly and no later than 10 working days after becoming aware of the event. Reports relating to the patient’s subsequent medical course must be submitted to the Sponsor and the reviewing IRB until the event has subsided or, in case of permanent impairment, until the event has stabilized, and the overall clinical outcome has been ascertained.

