5.1. Handling of Missing Neuro Assessment Data at the Final Analysis

All efforts will be put forth to ensure near complete follow-up is obtained, in particular with the assessment of the primary outcome (mRS at 90 days). The final analysis will be conducted when all subjects have reached the upper limit of the window for the 90-day follow-up window (105 days after index procedure), and when the study sites believe they have exhausted all reasonable efforts to obtain outcome data collected within the window.

Nevertheless, some missing data may result. Missing 90-day mRS data (no mRS available within a 75-105 day window) will be handled by imputing the 30-Day mRS. In the case of patient death prior to the completion of the 90-Day visit, the subject will be counted as a failure (mRS = 6).

Missing 90-day NIHSS data (no NIHSS available within a 75–105-day window) will be handled by imputing the 30-Day NIHSS. In the case of missed 30-day NIHSS or of potential death prior to the completion of the 90-Day visit, the last study reported NIHSS will be imputed for analysis.

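### Investigator termination or three failed contacts ends adverse event collection, and nothing continues new events, vital status, three-month nerve status or the 90-day mRS for patients who have not withdrawn consent

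*Protocol*

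**What the plan says.** Protocol Section 9.2 opens with a retention aim: "Where possible, every effort should be made for a patient to remain in the study until completion of the required follow-up period". It then lists ways in which participation may end. Two matter here.

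- Investigator termination: "The Investigator may terminate the patient's participation without regard to the patient's consent if the Investigator believes it is medically necessary".
- Loss to follow-up: "A patient will be considered lost to follow-up after three unsuccessful, documented attempts have been made to contact the patient". The rule gives no spacing of attempts, no visit, no link to the 90-day window and no alternate contact.

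In either case the section asks for a documented reason and a completed CRF, and for nothing further.

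Section 12 sets the AE collection period as "from index procedure through 90-day follow-up period (or until patient discontinuation) for all enrolled patients on the Adverse Event CRF". Section 10.3.3 adds: "Any adverse events that are observed after establishing reverse flow will be followed through study exit". For serious events, Section 12.2 requires reports on the later course "until the event has subsided or, in case of permanent impairment, until the event has stabilized". Sections 12.3 and 12.4 say much the same for serious and unanticipated device events.

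In the SAP, Section 5.1 runs the final analysis once all subjects have passed the window and "when the study sites believe they have exhausted all reasonable efforts to obtain outcome data collected within the window". It imputes the day-30 mRS for a missing 90-day mRS and scores death before the 90-day visit as mRS 6. Section 8 computes binary safety rates over all subjects, whatever their follow-up time.

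**The concern.** Once the procedure is over, what remains under the protocol is mainly assessment: neurological scales, imaging and AE recording. Ending participation at that stage chiefly ends data collection. Two primary outcomes depend on status at about three months: mRS 0-2 at 90 days, and permanent cranial nerve injury, which Appendix 4 defines by non-resolution at three months.

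If a patient leaves by investigator termination or by the contact rule without withdrawing consent, the plan does not say that these outcomes are still sought. The analysis rules then fill the gap. For safety, a patient with nothing recorded is counted as event-free. For function, the day-30 score stands in for an outcome nobody observed. The safety rates are then set numerically beside the ENROUTE program data (SAP Section 5), where a few events in about 30 patients would change the picture.

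**Working it through.** **Step 1. What survives discontinuation.** Setting the passages side by side:

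| Item | Collected after investigator termination or declared loss? | Source |
|---|---|---|
| SAE or device event already reported | Yes, until subsided or stabilized; no discontinuation cut-off stated | Protocol 12.2 to 12.4 |
| AE already observed, not serious | To study exit only | Protocol 10.3.3, 12 |
| New AE or SAE | No; collection ends at discontinuation | Protocol 12 |
| Vital status | No provision | none found |
| Cranial nerve status at three months | Only if the injury was already reported as serious | Appendix 4 with 12.2 |
| 90-day mRS | No provision | none found |

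The nerve-injury row has a particular weakness. One criterion for seriousness in 12.2 is permanent impairment, and permanence is judged at three months. An injury seen early may therefore not yet be reported as serious when the patient leaves.

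**Step 2. What the analysis does with the gap.**

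- Safety: the rate is (patients with a recorded event)/N, with N = all subjects. Missing collection can lower the numerator but never the denominator, so any error is toward a lower rate.
- mRS: a patient with mRS 2 at day 30 who leaves and then dies unrecorded is scored as a success, because the mRS 6 rule works only if the death is known. A patient at mRS 3 on day 30 who later improves is scored as a failure. The direction of error is therefore not fixed for mRS. If the day-30 mRS is also missing, SAP 5.1 gives no mRS rule, although it gives a last-value rule for NIHSS.

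**Step 3. Size.** The plan states no dropout rate, power or hypothesis test, so there is no figure of its own to reproduce. Let d be the number of patients leaving by these routes (an assumption). The gap between the best and worst case for a proportion is d/N:

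| N | d=1 | d=3 | d=5 |
|---|---|---|---|
| 30 (PP minimum) | 3.3 points | 10.0 | 16.7 |
| 40 (PP maximum) | 2.5 | 7.5 | 12.5 |
| 60 (ITT maximum) | 1.7 | 5.0 | 8.3 |

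For a safety rate with no recorded events at N=30, the exact 95% upper limit is 1 − 0.025^(1/30) = 11.6%. With d=3 the extreme case is 3/30 = 10.0%, whose exact upper limit is 26.5%. That extreme requires all three patients to have had an unseen event.

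A less extreme view takes a risk p of a late event per departed patient. The chance that at least one event is missed among three is 1 − (1 − p)^3, which is 14.3% for p = 5%, 27.1% for p = 10% and 48.8% for p = 20%. These values of p are also assumptions.

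**The case against.** The strongest reply is that the plan already mitigates this. Section 9.2 asks for every effort at retention, SAP 5.1 expects sites to exhaust reasonable efforts before the final analysis, and termination is conditional on medical necessity. Many access-related complications would plausibly appear before discharge, when collection is intact. The study is a feasibility study with no hypothesis test. All of this stands and limits the size of the problem. None of it says that outcomes are collected once a patient has been discontinued.

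A reader might also infer several stronger points that the documents do not support:

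- **That Section 12 contradicts 12.2 and 12.3.** Section 12 sets the period for collecting AEs; 12.2 to 12.4 set the duty to keep reporting on events already reported. The scopes differ. The wording should be aligned, but follow-up of a reported serious complication is not cut off.
- **That 9.2 undermines the independent-assessor rule.** Section 11 governs who performs the neurological examination. It does not address who may discontinue a patient.
- **That withdrawal is all-or-nothing.** Section 9.2 names two routes, refusal of all further testing and follow-up or withdrawal of consent, and the consent pages are not available for review. A patient's own withdrawal of consent properly ends collection and is not part of this point.
- **That patients with complications will be the ones terminated or lost.** This is plausible, but no passage shows it.
- **That three missed calls at day 30 will end follow-up.** The contact rule permits that reading, because it names no visit. It does not prescribe it, and the retention wording points the other way.
- **That termination can only ever end observation.** Enrollment under Section 9 precedes the transcarotid procedure, and imaging follows it, so stopping study procedures can have a medical purpose.

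**Conclusion.** The concern holds in a limited form. For patients who leave by investigator termination or failed contact without withdrawing consent, nothing continues collection of new AEs, vital status, three-month cranial nerve status or the 90-day mRS. Under the SAP's all-subject denominator the resulting error in safety rates can only be downward. For mRS it is an unobserved outcome replaced by an earlier one, with no fixed direction.

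Each such patient is worth up to 3.3 points at N=30 and 1.7 points at N=60. For safety this applies to late events only. The number of patients and their prognosis are assumptions, so these figures show what is possible rather than an expected bias.

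**What to change.** 1. **Protocol Section 12:** replace the clause that stops AE collection at discontinuation with one that stops it only when consent for follow-up is withdrawn. Align Section 10.3.3 and Sections 12.2 to 12.4 with that wording.
2. **Protocol Section 9.2:** state that investigator termination or missed contacts do not end collection of AEs, vital status and the 90-day mRS (by phone if needed) unless the patient or legally authorized representative withdraws consent for follow-up. Include cranial nerve status at three months. The investigator's authority to stop study procedures for medical reasons is left unchanged.
3. **Loss to follow-up:** declare it only once the 90-day window has closed, after attempts that include the representative, family or treating facility. State that a missed day-30 contact does not discontinue the patient. Name one closing day: the protocol's 90 + 14 gives day 104, while SAP 5.1 uses day 105.

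The cost is protocol and consent wording and a few extra calls, in a study of at most 60 patients.

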10.1 Informed Consent

Prior to patient participation in this study, the Investigator will obtain written Institutional Review Board (IRB) approval for the protocol and the informed consent form (ICF). The approved consent form should clearly reflect the IRB approval date and protocol version.

Written informed consent must be obtained for all patients who are screened and meet the general inclusion/exclusion criteria prior to enrollment. The patient or the patient's Legally Authorized Representative (as defined by the local IRB) will be asked to sign the informed consent form before any study-specific tests or procedures are performed. A copy of the signed and dated informed consent will be provided to the study patient and/or the Legally Authorized Representative (LAR).

The nature and scope of the study, potential risks and benefits of participation, any questions the patient and/or the LAR may have, are to be addressed by the Investigator or person designated by the Investigator who has been trained to the study protocol. The study will be explained to the study patient and/or the LAR in lay terms and native language. Study patients will be assured that they may withdraw from the study at any time and for any reason. Trained study staff should

explain that even if a patient agrees to participate in the study and signs an Informed Consent Form, noninvasive baseline imaging or cerebral angiography may demonstrate that the patient is not a suitable candidate for the study treatment.

A Screening and Enrollment Log will be maintained by the site to document basic information such as date screened and reason for screen failures for patients who fail to meet the study eligibility criteria. Screen failed subjects will not be entered into the electronic database or followed beyond the screening visit, and no further data will be collected/recorded.

10.2 Pre-Procedure

All patients will undergo imaging assessments, neurological evaluation, and review of his/her medical history to determine eligibility. If any of these tests do not fall within the Investigator's standard clinical practice, they should still be conducted for patients to be enrolled in the study.

The neurological assessment will include a pre-stroke mRS and a baseline NIH Stroke Scale (NIHSS).

10.2.1 Pre-Procedure Imaging

The suitability of the common carotid artery for direct access (as part of standard of care) must be measured by computerized axial tomography (CT) angiography of both head and neck in accordance with the product labeling.

A CT-Perfusion study (CTP) will also be completed to ensure imaging requirements for inclusion criteria are met (Section 8.3). The CTP imaging and report will be submitted by the sites for core lab and DSMB review.

10.3 Transcarotid Endovascular Therapy Procedure

10.3.1 Intra-Procedural Medications

All medications will be administered per institution standard of care for endovascular therapy procedures. All medications administered should be recorded on the patient's medical record. Pertinent medication given to the patient will be recorded on the Concomitant Medication Form, with clear indication to the procedural step at which the medication was administered, as applicable.

10.3.2 Failed Transfemoral Therapy

For the purposes of this study, failed transfemoral therapy is defined as either a unsuccessful transfemoral mechanical thrombectomy attempt made for at least 15 minutes having elapsed from groin puncture or inadequate or prohibitive anatomy deems a transfemoral approach not possible, as determined by the operator (see Appendix 4 for definition).

Reasons for failed transfemoral therapy should be documented both on the patient's medical record and study CRFs.

10.3.3 Establishment of Transcarotid Flow Reversal

The type of anesthesia used during the procedure is left to the discretion of the Investigator and will be documented on the CRFs. Should the investigator choose to start with moderate sedation conversion to general anesthetic should only occur if the Investigator deems it necessary. The type of anesthesia used will be documented in the CRFs.

After completing confirmatory duplex ultrasound, access to the common carotid artery cephalad to the clavicle will be gained using surgical techniques.

Investigators are to follow the NOVIS Transcarotid Neuroprotection System (NPS) Instructions for Use (IFU) for setting up and establishing the reverse flow circuit. Upon placement of the NOVIS system and prior to clamping the CCA, the differential in pressure causes some blood to flow between the CCA and femoral vein. At this point, there is still some antegrade flow in the CCA and therefore the carotid and cerebral vasculature is not “protected”. Once the CCA is clamped below the arterial sheath of the system on the Low flow setting, the NPS should remain on Low flow setting and switch to High flow upon the introduction of interventional tools through the completion of the procedure. Upon initial set-up of the device a pressurized, heparinized saline drip is connected to the 3-way stopcock on the side arm of the rotating hemostasis valve.

Any adverse events that are observed after establishing reverse flow will be followed through study exit.

